## 1 Study Information

### 1.1 Introduction

This is a randomized, multi-center, subject-blinded and evaluator-blinded study in China to evaluate the pain and the safety profile associated with correction of moderate to severe nasolabial folds (NLFs) using Restylane Lidocaine compared to Restylane. Approximately 70 subjects will be randomized to be treated with Restylane Lidocaine in one NLF and Restylane in the other, thus it is a split-face design. The study subjects will be treated at the baseline visit and thereafter followed for 2 weeks.

For more information regarding the study, please refer to the study protocol.

### 1.2 Study Objectives

#### 1.2.1 Primary Objective

The primary objective is to evaluate the pain associated with injections of Restylane Lidocaine compared to Restylane using a visual analogue scale (VAS).

The proportion of subjects that have a within-subject difference in VAS score (Restylane-Restylane Lidocaine) of at least 10 mm at injection will be calculated together with a two-sided 95% confidence interval. The objective is to show that the confidence interval lies above 50%.

#### 1.2.2 Secondary Objectives

The secondary objectives and endpoints are:

- To evaluate the pain associated with injections of Restylane Lidocaine compared to Restylane by assessment of
  - Proportion of subjects that have a within-subject difference in VAS score (Restylane-Restylane Lidocaine) of at least 10 mm (at 15, 30, 45 and 60 minutes after injection).

CCI

CCI

#### 1.2.3 Safety objectives

The safety objectives and endpoints are:

- To evaluate the safety of Restylane Lidocaine and Restylane during the whole study by collecting AEs.

 GALDERMA	<small>Title</small> 43CH1504 Restylane Lido Statistical Analysis Plan	<small>Doc id</small> MA-28883
--	--	--

CCI

### 1.3 Efficacy Endpoints

#### 1.3.1 Visual Analogue Scale (VAS)

The VAS is a subjective scale to measure pain intensity. The subject shall be instructed to put a vertical mark, approximating the pain experienced during the procedure, on a 100 mm horizontal line labeled “No pain” at the left end and “The worst pain you can imagine” at the right end. The distance in mm from the left end (no pain) to the subject’s VAS mark shall be measured with a standard ruler. Each NLF will be evaluated independently. Subjects will evaluate injection site pain for each side of the face at the time of injection (before massaging) and at 15, 30, 45, and 60 minutes post-treatment by completing a VAS.

Visual Analogue Scale (VAS)

No pain \_\_\_\_\_ The worst pain you can imagine.

Derived endpoints:

At each time point, the following variables will be derived:

- The within-subject difference in VAS scores, calculated as Restylane-Restylane Lidocaine.
- A dichotomous variable taking the value 1 if the within-subject difference in VAS scores is at least 10 mm, and 0 otherwise.

CCI

Effective date: 2016-05-04 09:07

*Effective*

Version: 1.0

 GALDERMA	Title 43CH1504 Restylane Lido Statistical Analysis Plan	Doc id MA-28883
--	---	---------------------------

CCI

## 1.4 Safety Assessments

The methods for collecting safety data are described in Section 8 of the Clinical Study Protocol (CSP) and include assessments of Injection site reactions in CCI, Adverse Events (AE), Serious Adverse Events (SAE), and Device Deficiency. Laboratory assessments and ECG will also be assessed, but at screening only.

### Derived variables

A two-point scale (“Yes” or “No” response) will be used for the causality assessments. The Treating Investigator should be asked to indicate a response to each of the following questions in the eCRF:

- “Do you consider that there is a reasonable possibility that the event may have been caused by the study product?”
- “Do you consider that there is a reasonable possibility that the event may have been caused by the injection procedure?”

	Title 43CH1504 Restylane Lido Statistical Analysis Plan	Doc id MA-28883
--	---	---------------------------

Effective date: 2016-05-04 09:07

Effective

Version: 1.0

If any of these questions is answered with a 'Yes', the AE will be considered related. These assessments will also be reviewed by the Sponsor. In the case of a disagreement, the AE will be classified as "Related".

Time to onset of an AE will be derived as the start date minus Day 1. If the start date is missing, it will be assumed that the AE started on Day 1.

Duration of an AE will be derived as the stop date minus the start date + 1. If the start date is missing, it will be assumed that the AE started on Day 1. Missing stop date will not be imputed and therefore no duration will be calculated in these cases. Instead, the number of AEs that were ongoing at the end of the study will be given.

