8.4.3 Recording Instructions

AE will begin to be collected after ICF signed. Each subject will be questioned about AEs at each clinical visit following the screening visit. The question asked will be "Since your last clinical visit have you had any health problems?" Information on AEs can also be obtained

from signs and symptoms detected during each examination or from a laboratory test, observations by the study personnel, **CCI** or spontaneous reports from the subjects.

When an AE is related to a device deficiency (refer to section 8.5), including technical device malfunction, the AE shall be recorded on the AE module in the eCRF and the technical complaint shall be reported separately on the clinical study complaint form.

Investigators, or other study personnel, will record all AEs in the eCRF, including:

- Event term (recorded in standard medical terminology and avoiding abbreviations),
- Description of event and affected area (if applicable),
- Start date (First day with symptoms)
- Stop date (Last day with symptoms)
- Intensity (mild, moderate or severe according to definition in section 8.4.3.1)
- Seriousness (serious or not serious, according to definition in section 8.4.2)
- Causal relationship to study product and study product injection procedure (yes or no)
- Action taken (none, medication treatment, non-pharmacological treatment or other procedures/ tests, subject withdrawn)
- Outcome of the AE (ongoing, recovered, recovered with sequele, death, chronic/ stable, not recovered at study end)

The AE module in the eCRF must be signed and dated by the Investigator.

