8.4.6 Follow-up of Unresolved Events after study termination

All serious as well as non-serious AEs with a causal relationship to the study product or treatment procedure and ongoing at study end, shall be followed up after the subject's participation in the study is over. Such events shall be followed-up after the last study visit until resolved, assessed as chronic or stable, or for at least three months. Final outcome after study end should be reported on an AE Follow-up module in the eCRF.

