8.4.8 Anticipated Adverse Events

After the injection some common injection-related reactions might occur with both products. These reactions include bruising, erythema, swelling, pain, tenderness and itching at the injections site. Typically these reactions start on the day of treatment and resolve spontaneous within a few days after injection, as observed in the Chinese clinical study for Restylane and in consistent with international results for both products.

Refer to the Restylane Lidocaine EU IFU and Restylane China IFU.

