9.1 Data management

Data management based on GCP refers to the activities defined to achieve safe routines to enter clinical data information into a database, efficiently and avoiding errors. The data management routine includes procedures for handling eCRFs, database set-up and management, data entry and verification, data validation, and documentation of the performed activities including information of discrepancies in the process. The data management process will be described in detail in the data management plan (DMP).

The database, the data entry screens and program will be designed in accordance with the CSP. Data validation will be performed by computerised logical checks and manual review. Drugs and events will be coded in accordance with World Health Organization (WHO) Drug and medical dictionary for regulatory activities (MedDRA) dictionaries as specified in the DMP. Safety data (SAE) in the clinical database will be reconciled against the data in the safety database.

When all efforts have been made to ensure that the data recorded in the eCRFs and entered in the database is as correct and complete as possible, the clinical database will be locked. Study data will be transferred to SAS datasets which thereafter will be write-protected. Statistical analyses will be generated in SAS using data from the locked datasets.

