10.5 Safety Analysis

CCI

A similar summary will also be presented by severity. A graph will be generated to illustrate the incidence over time.

All AEs will be coded according to MedDRA. All AEs will be summarised by system organ class (SOC) and preferred term (PT). The same summaries will be generated for related AEs, severe AEs, AEs leading to discontinuation, and serious AEs. For related AEs, the number of days to onset and the duration of event will be summarised by SOC and PT using mean, SD, min, max and median statistics.

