## 2.9 Safety Analysis

All safety evaluations will be performed based on the safety analysis set.

AEs will be summarized in frequency tables by group, presenting number of subjects with no AEs and subjects with at least one AE subdivided by related/unrelated, and serious/non-serious. All AEs will be summarized and listed by SOC and PT assigned using MedDRA. Furthermore, AEs will be summarized by causality and maximum intensity. For related AEs the number of days to onset and the duration of the event will be summarized by PT.

All AEs will be included in the data listings. Any serious adverse events and/or AEs that led to withdrawal will be listed separately.

	
Title 43CH1504 Restylane Lido Statistical Analysis Plan
	
Doc id MA-28883

--	--	-----------------------------------

Effective date: 2016-05-04 09:07

*Effective*

Version: 1.0

CCI

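### Does leaving adverse events without a stop date out of the duration statistics call for a change to the SAP?

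*SAP*

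**What the plan says.** SAP 1.4 (Derived variables) defines the duration of an AE as stop date − start date + 1, in days. For events with no stop date it says "Missing stop date will not be imputed and therefore no duration will be calculated in these cases", and then "Instead, the number of AEs that were ongoing at the end of the study will be given".

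The result is used in SAP 2.9: "For related AEs the number of days to onset and the duration of the event will be summarized by PT". Protocol 10.5 names the statistics: "the duration of event will be summarised by SOC and PT using mean, SD, min, max and median statistics". The readable SAP text names only mean, median and standard deviation, as examples, in section 2.1; minimum and maximum come from the protocol alone. SAP 2.1 and 2.9 put all study data, and all AEs, in listings.

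Three protocol sections bear on which events lack a stop date. Section 8.4.3 lists the possible outcomes: "Outcome of the AE (ongoing, recovered, recovered with sequele, death, chronic/ stable, not recovered at study end". Section 8.4.6 has related AEs that are open at study end followed further, and adds: "Final outcome after study end should be reported on an AE Follow-up module in the eCRF". Section 9.1 says: "Statistical analyses will be generated in SAS using data from the locked datasets". Parts of Protocol 10.5 and SAP 2.9 are redacted, so any silence noted here is silence of the readable text.

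**The concern.** An event that has not resolved is dropped from the mean, SD, median and maximum because it lasted longer than observation. Omission therefore depends on the quantity being summarised, and the error has a known direction: reported durations are too short. The maximum suffers most, since it becomes the longest resolved event.

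Two details also look open. The SAP does not say whether a stop date obtained after the final visit, through the AE Follow-up module, enters the formula. It also does not say which of the three unresolved outcomes (ongoing, chronic/stable, not recovered at study end) make up the ongoing count, or where an event recorded as recovered with an unknown stop date belongs. If this mattered, readers could take the duration table as evidence that related reactions are shorter-lived than they are, and two programmers could produce different tables from the same database.

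**Working it through.** The documents state no mean duration and no unresolved share, so there is no figure of the plan's to reproduce. What can be checked is the reach of the rule and the size of the shortfall over an assumed range.

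**1. Longest duration that can be reported, Day 1 onset.** The final visit is on Day 15 (+3 days).
- Stop dates up to the final visit only: 15 − 1 + 1 = 15 days, or 18 − 1 + 1 = 18 days.
- Stop dates from later follow-up as well, taking the three months of Protocol 8.4.6 as 90 days (an assumption): 15 + 90 = 105, or 18 + 90 = 108 days.

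**2. Shortfall under the less favourable reading (no later stop dates).** Assume exponential durations with true mean m, onset on Day 1, cut-off c = 15 or 18 days, and p = exp(−c/m).
- Share unresolved: p
- Mean of resolved events: m − c·p/(1 − p)
- Median of resolved events: −m·ln(1 − 0.5(1 − p))
- True median: m·ln 2

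For m = 3 and c = 15: p = exp(−5) = 0.0067; mean = 3 − 15 × 0.0067/0.9933 = 2.90; median = 2.06 against a true 2.08.

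| True mean (days) | Unresolved, c = 15 / 18 | Resolved-only mean | Mean short by | Resolved-only median (true) |
|---|---|---|---|---|
| 3 | 0.7% / 0.2% | 2.90 / 2.96 | 3% / 1% | 2.06 / 2.07 (2.08) |
| 5 | 5.0% / 2.7% | 4.21 / 4.49 | 16% / 10% | 3.22 / 3.33 (3.47) |
| 7 | 11.7% / 7.6% | 5.01 / 5.51 | 28% / 21% | 4.08 / 4.34 (4.85) |
| 10 | 22.3% / 16.5% | 5.69 / 6.44 | 43% / 36% | 4.92 / 5.40 (6.93) |

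**3. Which row applies.** Protocol 8.4.8 says of the anticipated reactions: "Typically these reactions start on the day of treatment and resolve spontaneous within a few days after injection". The 3-day row is closest to that. There the median moves by 0.01 to 0.02 day, which is nothing on a whole-day scale. No passage supports means of 7 or 10 days.

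**4. A count-based illustration (assumed numbers).** Take 20 related AEs of one preferred term: 18 resolved, three at each of 2, 3, 4, 5, 6 and 7 days, and 2 open at Day 15. The SAP rule gives mean 4.5, median 4.5, maximum 7. Entering the two open events at their minimum of 15 days gives mean (18 × 4.5 + 2 × 15)/20 = 111/20 = 5.55, median 5.0, maximum 15. The mean and maximum move visibly, the median by half a day. Under the SAP the two events would appear in the ongoing count and in the listings.

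**5. The two open details.** The rule turns on whether the stop date is missing. The Follow-up module is part of the eCRF and the analyses use the locked data, so a stop date present at lock is not missing and enters the formula. If the module records only an outcome, or no date has arrived by lock, the event stays without a duration and in the count. The three unresolved outcomes in Protocol 8.4.3 all describe an event still open at study end, so a count of ongoing events takes them in. An event recorded as recovered is not ongoing; with an unknown stop date it has no duration and is seen in the listing.

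**The case for a change.** The best case for amending the SAP is this. Safety is a stated objective, and Protocol 2.5 relies on a two-week study as adequate to confirm the safety of adding lidocaine, so events lasting beyond two weeks are those a safety reader most wants to see, and the rule removes exactly these from the duration statistics. A single overall count would not show which preferred term or product is affected. The remedy would cost a few sentences: say that follow-up stop dates count, place the unresolved count by term and product beside the statistics, and treat open events as censored, with Kaplan-Meier medians where numbers allow.

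Part of this stands. The statistics do describe resolved events only, the direction of the error is as stated, and the readable text does not fix the layout of the count. The rest does not carry a change. The first two remedies write down what an analyst would do anyway when building the table, and the layout may be covered in redacted text. Kaplan-Meier estimation by preferred term, in about 70 subjects treated on both sides of the face and possibly with repeated events, needs an arbitrary threshold and raises clustering questions; it is a debatable alternative to a convention that is prespecified and disclosed. Nor are unresolved events always the longest: one starting on Day 13 and open on Day 15 has been observed for only 15 − 13 + 1 = 3 days. Both products are injected in the same subject on the same day with the same final visit, so the cut-off is common to both sides.

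**Conclusion.** No change to the plan is needed. The rule summarises duration for resolved events and counts the unresolved ones separately, which is a fair and openly stated trade-off for a descriptive safety table. In the setting the protocol expects, the reported mean is 1% to 3% short and the median is in effect unchanged. The shortfall reaches 36% to 43% only if the true mean is 10 days, and then 16.5% to 22.3% of events would be open at the final visit and the ongoing count would warn the reader. These figures rest on exponential durations, Day 1 onset and no stop dates after the final visit; if follow-up dates are used, as a plain reading allows, the shortfall is smaller. The gaps about follow-up dates and outcome categories are ones that analysts fill sensibly from the existing text. No test of duration is visible, and the primary endpoint does not depend on any of this.

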## 2 Statistical Methods

### 2.1 General

All statistical analyses, including summary tables and data listings, will be performed using the SAS® system (version 9).

Confidence intervals will be 2-sided and made at the 95% confidence level. **CCI**

Continuous or semi-continuous variables will be summarized using descriptive statistics, e.g. mean, median and standard deviation. Categorical variables will be presented in frequency tables with number (n) and percent of observations for each level. All study data will be listed in subject listings.

Baseline value is defined as the latest measurement taken prior to treatment on Day 1.

### 2.2 Disposition of subjects

The disposition of subjects will be presented by the treatment group, and in total, including numbers of subjects that were:

- Screened
- Randomized
- Treated
- Completed
- Withdrawn

These numbers may also be presented by center. The number of completed and withdrawn subjects will also be presented by visit. Reasons for screening failures, if applicable, will be summarized.

In addition, the number of subjects in each analysis population set (see Section 2.6) will be presented by center and in total.

### 2.3 Withdrawals and Protocol Deviations

All withdrawn subjects will be listed individually, including at least subject number, date and reason for withdrawal, and last visit performed. Subjects with CSP deviations will be listed individually, including subject number and observed deviation. Depending on the seriousness of the

	
Title 43CH1504 Restylane Lido Statistical Analysis Plan
	
Doc id MA-28883

--	---	-----------------------------------

deviation, subject might be excluded from the Per Protocol (PP) population, which shall be documented prior to database lock. For this study, the following protocol deviations that will exclude subjects from PP are identified (but not limited to):

- VAS assessment at injection missing for at least one side
- Study products not administered according to randomization

CCI

Deviations from the Statistical Analysis Plan (SAP) will be documented in the protocol deviation log.

## 2.4 Treatment procedure

Data related to study treatment will be summarized by means of descriptive statistics and/or subject listings as appropriate using the Intention-To-Treat (ITT) analysis set, as defined in Section 2.6.

Injection technique or procedure applied, administered volume, and any technical problems (Device Deficiencies) will be summarized by treatment.

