8.5 Device Deficiencies

8.5.1 Definition of Device Deficiency

A device deficiency is defined as an inadequacy of a medical device with respect to its identity, quality, durability, reliability, safety* or performance.

Note: Device deficiencies include malfunctions, use errors, and inadequate labelling.

*Inadequacy of device safety refers to properties of the device which could have or have led to an AE.

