## 2.6 Analysis Populations

The following analysis sets will be defined:

- Safety analysis set Includes all subjects who were injected in at least one NLF, based on the as treated principle.
- Intention To Treat (ITT) Includes all subjects who were injected in both NLFs. Subjects are analyzed according to the randomization assignment.
- Per Protocol (PP) Includes all ITT subjects who completed the VAS assessment at injection without any deviations considered to have substantial impact on the primary efficacy outcome.

The ITT population is the primary population for all efficacy analyses. All safety analyses will be based on the Safety population.

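### SAP 2.4 summarises device deficiencies and administered volume on the ITT set, although the plan's own rule sends safety data to the Safety set

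*SAP*

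**What the plan says.** SAP 2.4 covers the treatment procedure. It summarises study-treatment data "using the Intention-To-Treat (ITT) analysis set, as defined in Section 2.6". The next paragraph of the same section gives the content of the by-treatment summary: injection technique, administered volume, and device deficiencies ("any technical problems (Device Deficiencies) will be summarized by treatment"). It names no other analysis set.

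SAP 2.6 defines the two sets that matter here:

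- ITT: "Includes all subjects who were injected in both NLFs. Subjects are analyzed according to the randomization assignment".
- Safety: "Includes all subjects who were injected in at least one NLF, based on the as treated principle".

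SAP 2.6 then adds: "All safety analyses will be based on the Safety population". SAP 2.9 repeats that rule for safety evaluations, and Protocol 10.2 has the same definitions and the same rule.

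Device deficiency is safety data under the plan. SAP 1.4 ends its list of safety assessments with "Serious Adverse Events (SAE), and Device Deficiency", and Protocol 8.5 sits in the Safety Assessments chapter. The definition is broad: "Device deficiencies include malfunctions, use errors, and inadequate labelling" (Protocol 8.5.1).

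SAP 2.12, which records departures from the protocol's analysis, mentions only the SAS version.

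**The concern.** The plan gives one rule for safety data and a different one for this item of safety data, without declaring the difference. The two sets differ in ways that bear on deficiencies in particular.

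First, ITT membership requires injection in both folds. The folds are treated in sequence, right then left, 20 ± 5 minutes apart (Protocol 4.1). A deficiency that prevents the left injection therefore removes the subject from the set on which deficiencies are summarised, so inclusion depends on the event being counted.

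Second, ITT attributes data by randomised assignment. Use errors and labelling faults count as deficiencies, and either could put a product in the wrong fold. A by-treatment table is informative only if each event sits under the product it concerns.

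Comparing the safety profiles of the two products is a stated purpose of the trial, so exposure, deficiencies and adverse events should rest on the same subjects and the same attribution rule.

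**Working it through.** The plan states no figure on this point, so there is none to reproduce. The check applies the SAP 2.6 definitions to the situations that could arise.

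| Situation | ITT (SAP 2.4 as written) | Safety set (SAP 2.6, 2.9) |
|---|---|---|
| A. Right fold injected; a deficiency means the left fold is never injected | Subject excluded, event absent from the summary | Subject included |
| B. Left injection started, then interrupted by a deficiency | Included (both folds injected) | Included |
| C. Deficiency found before any injection; neither fold injected | Excluded | Excluded |
| D. Both folds injected, products swapped | Included, tabulated under the assigned product | Included, tabulated under the product used |

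**Situation A.** The planned number is about 70 subjects (Protocol 4.2, SAP 1.1). As an assumption for illustration only, let 70 subjects be treated, let k of them be in situation A, and let there be no other deficiency. At subject level, with the products pooled:

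- ITT summary: 0 of (70 − k).
- Safety summary: k of 70.
- k = 1: 0 of 69 against 1 of 70 (1/70 = 1.4%).
- k = 3: 0 of 67 against 3 of 70 (3/70 = 4.3%).

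The values of k are assumed; nothing in the documents says what k would be, and it may be 0. The figures are also not per-product rates. A subject whose left fold was never injected did not receive the second product, so that product's as-treated denominator is smaller than 70. With k = 1 it is 70 − 1 = 69. Counts by product are therefore safer than percentages.

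**Situation D.** SAP 2.3 foresees administration contrary to randomisation and makes it a reason for exclusion from the per-protocol set. It states no exclusion from ITT, so the subject stays in the SAP 2.4 summary under the assigned product for each fold. Under SAP 2.9, the same subject's adverse events follow the product received. Exposure and adverse events for one fold would then point to opposite products.

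**Situation C** shows the limit of simply exchanging one set for the other: neither set contains a subject in whom no fold was injected. A related gap remains in A. The failed syringe belonged to a product that the subject never received, so an as-treated rule alone does not say where to count it.

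**The case against.** Several points on the other side have force.

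- **The events are not lost from reporting.** SAP 2.1 lists all study data by subject. Protocol 8.5.2 and 8.5.3 require a complaint form for each deficiency, assessment by both investigator and sponsor of whether it could have led to a serious event, and reporting within 24 hours where it did or could have. A resulting adverse event is summarised on the Safety set. This stands. A reader might infer that the most serious deficiencies vanish, but the documents support only their absence from one descriptive summary.
- **It may not be the only summary.** The end of SAP 2.9 is redacted. A reader might infer from the visible text that SAP 2.4 holds the sole deficiency table; that cannot be established. A further table would still leave the wording of SAP 2.4 in conflict with SAP 2.6.
- **The wording leaves room.** The ITT sentence and the deficiency sentence are separate paragraphs, and a programmer who read SAP 1.4 with SAP 2.9 might choose the Safety set. That is possible, but both sentences stand in SAP 2.4, and ITT is the only set named there. Text that two programmers could implement differently needs settling in any case.
- **Situation A is narrow.** The left fold must receive no injection at all. Two needles are provided for each product (Protocol 6.3), and the protocol provides for checking a needle that meets resistance (Protocol 6.6.1). The documents give no sign that the event is likely.
- **Situation D may move little.** A reader might infer that every use error is credited to the wrong product. Only errors that put a product in the fold assigned to the other are affected, and such deviations are listed individually. Since Protocol 6.6.2 prefers equal volumes in the two folds, a swap would change mean volume by product only slightly.
- **Exposure on ITT is partly convention**, alongside the baseline data in SAP 2.5. That is fair for volume alone, but it does not extend to deficiencies, which the SAP itself classes as safety data.

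**Conclusion.** The inconsistency is real. SAP 2.4, as written, applies the ITT set to an item that SAP 1.4 classes as safety data and that SAP 2.6, SAP 2.9 and Protocol 10.2 assign to the Safety set. Two consequences follow from the definitions: a deficiency that leaves the left fold entirely uninjected drops out of the SAP 2.4 summary, and after a product swap the deficiency and the volume are tabulated under the product not used in that fold.

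The size is limited to that descriptive summary. No event rate, and so no percentage under-count, can be derived from the documents; the illustration rests on assumed counts. The primary efficacy result, the adverse event tables and the listings are untouched. Nor should a reader infer that substituting the Safety set is sufficient by itself: situation C and the never-injected syringe in situation A need a separate counting rule. Severity is minor to moderate. It is worth correcting because the choice of set should be settled before the data are seen.

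**What to change.** In SAP 2.4:

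1. Name the Safety analysis set (as treated) for administered volume and device deficiencies in place of ITT.
2. Tabulate device deficiencies as counts by the product actually in the syringe.
3. Include deficiencies found on any opened syringe in any randomised subject, even if that syringe, or any syringe, was not injected.

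The cost is one or two SAP sentences and a population change in two tables. No new data are needed: deficiencies and volume per fold already go into the eCRF (Protocol 6.6.5, 8.5.2), and dispensing logs record product and subject (Protocol 6.5). The change brings SAP 2.4 into line with SAP 1.4, 2.6 and 2.9 and with Protocol 10.2.
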